^a Subjects must sign informed consent for OL-RD cohorts prior to rescreening procedures. Rescreening for OL-RD can be completed at the SAD EOS 1 Day 90 Visit (Table 4); in this situation, the assessments in common should not be duplicated. The ISV includes 3 consecutive days of nutrition diary collection. A dietitian will review these 3 days of data and all nutrition data from the subject's prior participation in a SAD cohort to determine if the subject's diet meets nutritional guidelines and has been stable. If no nutritional changes are needed, subjects can proceed to OL-RD STV as soon as ISV assessments are completed. If nutrition changes are needed, NOVs occur as needed during the following week (approximately 2 weeks after the ISV). After 1 week of nutrition optimization, the subject proceeds to the STV (occurring approximately 2 weeks before the subject's OL-RD Baseline/Week 0 Visit) and thereafter maintains a stable diet as defined by the nutritional guidelines for GSD III. If a subject is unable to achieve an optimized diet within 2 weeks of the ISV, they are still eligible to proceed to the STV; the reason for inability to achieve an optimized diet should be documented and a stable diet should be maintained throughout the rest of the study. Figure 2 provides guidance on which screening visits are required for a given subject. All Rescreening Visits can be done remotely, with the exception of completion of imaging assessments (liver MRI, liver MRS, Fibroscan or ultrasound elastography) which must be completed in person at anytime during rescreening.

^b In the event a subject has an ET, all efforts will be made to monitor the subject through the end of the study. At minimum, a safety follow-up phone call will occur within the 4 weeks following the subject's last treatment.

^c Complete physical exam is required at rescreening (SAD EOS I Day 90 Visit), W0, and EOS II W48/ET. Targeted physical exams may be performed at W4, W8, W12, and W16.

^d Assessments to be performed prior to dosing on the same day as dosing visits or on the day before dosing for visits that include a CFC (ie, W16). When applicable, the following assessments can be collected within a week prior to dosing: HHD, PROMIS questionnaires, SF-36v2, and GNEM-FAS expanded version.

^e Refer to [Table 7](#) for the timing of vital sign assessments during dosing.

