Nutrition optimization		X																		
Nutrition stabilization			X																	
Randomization				X																
Drug Administration				X		X		X		X		X		X						
General Assessments																				
General & GSD III-specific medical history	X																			
COVID-19 testing	X																			
Demographics	X																			
Physical exam ^c	X		X	X ^d		X ^d		X ^d		X ^d		X ^d		X				X		
Vital signs	X		X	X ^e	X	X ^e	X	X ^e	X	X ^e	X	X ^e	X	X	X	X	X	X		
Height	X			X																
Weight	X		X	X ^d		X ^d		X ^d		X ^d		X ^d		X				X		
Adverse events	X	X	X	X	X	X	X	X	X	X	X	X	X	X	X	X	X	X		
Concomitant medications	X	X	X	X	X	X	X	X	X	X	X	X	X	X	X	X	X	X		
Pregnancy	X		X	X ^d				X ^d				X ^d		X		X	X	X		
ATX95					X ^f	X ^f	X ^f						X ^f	X ^f	X ^f	X ^f				
AGL mRNA					X ^f	X ^f	X ^f						X ^f	X ^f	X ^f	X ^f				
Anti-drug antibodies					X ^d		X ^d		X ^d		X ^d		X ^d		X		X	X		
Hepatitis B & C	X																			
Hemoglobin A1C	X															X		X		
Serum CH50, AH50, sC5b-9, & IL-6					X ^g		X ^g		X ^g		X ^g		X ^g	X	X					
Plasma fibrinogen & d-dimer					X ^g		X ^g		X ^g		X ^g		X ^g	X	X					
Hematology	X	X ^h	X	X ^d	X	X ^d	X	X ^d	X	X ^d	X	X ^d	X	X ^d	X	X	X	X		
Chemistry ⁱ	X	X ^h	X	X ^d	X	X ^d	X	X ^d	X	X ^d	X	X ^d	X	X ^d	X	X	X	X		
Urinalysis ^j	X	X ^h	X	X ^d	X	X ^d	X	X ^d	X	X ^d	X	X ^d	X	X ^d	X	X	X	X		
Serum CRP					X ^d	X	X ^d	X	X ^d	X	X ^d	X	X ^d	X	X	X	X	X		

Week (W)	Screening			BL/ W0	Treatment Period										Follow-up Period				EOS III (W48)/ ET ^b
	ISV ^a	NOV ^a	STV ^a		W1	W2	W3	W4	W5	W6	W7	W8	W9	W10	W12	W24	W36		
Visit Window Relative to Baseline	-	-	-	-	± 1 day	± 2 days										± 3 days			
Liver																			
Liver MRI ^k		X ^k													X				
Liver MRS ^k		X ^k													X				
FibroScan or ultrasound elastography ^k		X ^k													X				
PT/INR ⁱ	X		X	X ^d	X	X ^d	X	X ^d	X	X ^d	X	X ^d	X	X	X	X	X		
Serum HDL & LDL ^l	X	X ^h	X	X ^d										X	X	X	X		
Cardiac																			
Serum CK-M/B			X	X ^d		X		X		X		X		X	X	X	X		
Plasma BNP		X ^h	X	X ^d		X		X		X		X		X	X	X	X		
Serum troponin I			X	X ^d		X		X		X		X		X	X	X	X		
ECG	X			X ^d								X ^d					X		
Skeletal & Muscle Strength																			
Serum CK	X	X ^h	X	X ^d		X		X		X		X		X	X	X	X		
HHD			X	X ^d										X			X		
Clinician- & Patient-reported Outcomes																			
PROMIS questionnaires & SF-36v2				X ^d											X			X	
GNEM-FAS expanded version				X ^d											X			X	

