Nutrition diary	X ^m	X ^m	X ^m	X ^m	X ^m	X ^m	X ^m	X ^m	X ^m	X ^m	X ^m	X ^m	X ^m	X ^m	X ^m	X ^m	X ^m		
Exploratory Assessments																			
CFC and associated labs ⁿ			X ⁿ												X ⁿ				
Capillary ketones ^o	X		X ^o	X ^d		X ^d		X ^d		X ^d		X ^d		X ^o				X	
CGM ^p	X ^p	X ^p	X ^p	X ^p	X ^p	X ^p	X ^p	X ^p	X ^p	X ^p	X ^p	X ^p	X ^p	X ^p	X ^p	X ^p	X ^p		
Urine Glc ^q			X	X ^d	X	X ^d	X	X ^d	X	X ^d	X	X ^d	X	X	X	X	X		
AGL variant analysis	X																		
WBC, RBC, Serum & Plasma for Future Use ^q				X ^d	X		X							X		X		X	

Footnotes continue on the following page.

^a The ISV includes a review of the subject's diet. Within the first 2 weeks after the ISV, the Investigator will review nutrition diary data to determine if nutrition optimization is needed. If nutrition optimization is not needed, the STV occurs in clinic approximately 2 weeks after the ISV, and the Baseline/Week 0 Visit occurs approximately 6 weeks after the STV. If nutrition changes are needed, a 2- to 4-week period of nutrition optimization will be performed. The first

NOV occurs as a phone visit approximately 2 weeks after the ISV; during nutrition optimization, NOVs can occur weekly or more frequently as needed. When the Investigator determines that the subject has achieved nutritional optimization the STV is performed. [Figure 3](#) provides a schematic of screening for DB-RD cohorts.

^b In the event a subject has an ET, all efforts will be made to monitor the subject through the end of the study. At minimum, a safety follow-up phone call will occur within the 4 weeks following the subject's last treatment.

^c Complete physical exam is required at ISV, BL/W0, W2, and EOS III W48/ET. Targeted physical exams may be performed at STV, W4, W6, W8, and W10.

^d Assessments to be performed prior to dosing on the same day as dosing visits or on the day before dosing for visits that include a CFC (ie, W10). When applicable, the following assessments can be collected within a week prior to dosing: HHD, PROMIS questionnaires, SF-36v2, and GNEM-FAS expanded version.

^e Refer to [Table 7](#) for the timing of vital sign assessments during dosing.

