The first day of the ISV (which may coincide with the SAD Day 90 Visit) is followed by 3 consecutive days of nutrition diary collection. If a subject's diet during participation in a SAD cohort meets nutritional guidelines, and continues to do so at the ISV, the subject can proceed directly to the OL-RD Nutrition Stabilization Visit (STV) as soon as the ISV assessments are completed.

If the subject's diet does not meet nutritional guidelines, a Nutrition Optimization Visit (NOV) is performed. At this visit, nutritional counseling is provided to the subject on dietary changes needed to comply with GSD III-specific nutrition guidelines ([Table 2](#)). Nutrition diary and continuous glucose monitor (CGM) data will be reviewed by the Investigator and safety

laboratory tests may be obtained at the discretion of the Investigator. After 1 week of nutrition optimization (approximately 2 weeks after the ISV), the subject proceeds to the STV (occurring approximately 2 weeks before the subject's OL-RD Baseline/Week 0 Visit) and thereafter maintains a stable diet as defined by the nutritional guidelines for GSD III ([Table 2](#)) for the remainder of the study. If an OL-RD subject is unable to achieve an optimized diet, they are still eligible to proceed to the STV. The reason for the inability to achieve an optimized diet should be documented and the subject should make no substantial nutrition changes for the remainder of the study.

For selected sites and subjects, the OL-RD STV includes an optional controlled fasting challenge (CFC). Prior to the CFC, a morning cortisol is obtained between 6 and 9 am. The CFC is conducted during the subject's stay in the hospital, usually overnight, but can be conducted during the day. For the same sites and subjects, another optional CFC occurs at the Week 16 Visit; only subjects who completed the optional CFC at STV complete the CFC at Week 16. Additional details regarding the CFC are in Section [10.5.1](#).

Beginning with the OL-RD Baseline/Week 0 Visit, subjects in the OL-RD cohorts will receive 4 additional OL doses of UX053 Q4W at the same or lower dose than they received in the SAD cohorts, based on ongoing assessment of safety data.

Randomized, Double-Blind, and Placebo Controlled Cohorts

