For selected sites and subjects, the DB-RD STV includes an optional controlled fasting challenge (CFC). Prior to the CFC, a morning cortisol is obtained between 6 and 9 am. The CFC is conducted during the subject's stay in the hospital, usually overnight, but can be conducted during the day. For the same sites and subjects, another optional CFC occurs at the Week 10 Visit; only subjects who completed the optional CFC at STV complete the CFC at Week 10. Additional details regarding the CFC are in Section [10.5.1](#).

In DB-RD cohorts, treatment-naive subjects will be randomized 3:1 to UX053 or placebo in ascending dose cohorts (4 subjects per cohort) ([Figure 1](#)). DB-RD subjects will receive study drug Q2W; a total of 5 doses of study drug are planned. The planned dose levels are 0.05 mg/kg in cohort DB-1R, 0.10 mg/kg in cohort DB-2R, and 0.20 mg/kg in cohort DB-3R.

Initiation of RD Cohorts (Both OL-RD and DB-RD)

Initiation of RD cohorts is as follows:

- Initiation of Cohort DB-1R and OL-1R will be guided by DMC review of at least 2 weeks of safety data from at least 2 Cohort 2S subjects and any available data from all subjects in prior and ongoing cohorts.
- Initiation of Cohort OL-2R and DB-2R will be guided by DMC review of either 1) at least 6 weeks of safety data from at least 4 subjects within Cohort DB-1R or 2) at least 12 weeks of safety data from at least 3 subjects within Cohort OL-1R (whichever is available first). In both of these scenarios, all available data from all subjects in prior and ongoing cohorts will also be reviewed.
- Initiation of Cohort OL-3R and Cohort DB-3R will be guided by DMC review of either 1) at least 6 weeks of safety data from at least 4 subjects within Cohort DB-2R or 2) at least 12 weeks of safety data from at least 3 subjects within Cohort OL-2R (whichever is available first). In both of these scenarios, all available data from all subjects in prior and ongoing cohorts will also be reviewed.

Cohort- and Subject-level Dose Selection and Modification for All Cohorts (SAD, OL-RD, and DB-RD)

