7.1.4. Dose Rationale

The planned doses of UX053 (0.05, 0.10, and 0.20 mg/kg) aim to establish a safe dose of UX053 in adults with GSD III, as well as provide a preliminary PK and PD profile of UX053. These doses were chosen based on single-dose and repeat-dose pharmacology studies in mouse and dog models of GSD III, and RD toxicology and toxicokinetic studies in rats, cynomolgus monkeys, and Beagle dogs. The NOAEL in repeat-dose studies with 5 total doses of UX053 administered Q2W was **CCI** mg/kg in dogs, **CCI** mg/kg in rats, and **CCI** mg/kg in monkeys. The maximum tolerated dose (MTD) was **CCI** mg/kg in rats and **CCI** mg/kg in monkeys. The MTD in dogs is not known since higher doses were not evaluated with Q2W administration. The MTD in dogs with weekly dosing of UX053 is **CCI** mg/kg, but this short interval between doses is believed to promote an accumulation of toxicity that does not occur with Q2W dosing. Hence, the MTD in dogs may be greater than **CCI** mg/kg when UX053 is administered Q2W, but remains undetermined. **CCI**

Taken together, these PK and drug metabolism properties of the drug support 1:1 weight-based scaling from nonclinical species to humans, which is an approach endorsed by a cross-industry consortium of experts in oligonucleotide therapies, the Oligonucleotide Safety Working Group (Kornbrust, 2019; Marlowe et al., 2017). The FIH starting dose of 0.05 mg/kg is **CCI** less than the NOAEL in the most sensitive nonclinical species, the dog. The highest potential FIH dose of 0.30 mg/kg is **CCI** less than the dog NOAEL. Additional details regarding the use of weight-based scaling versus body-surface area scaling, as well as summaries of nonclinical studies with UX053 are available in the IB.

Sequential dosing with an interval of 72 hours between subjects' first dose within a cohort and a 2-week minimum review of data between cohorts was chosen to allow enough time to detect any potential TEAEs, including potential immune responses. In nonclinical studies, toxicities generally occurred soon after dosing and promptly resolved. The DB-RD cohorts will aim to achieve a steady state with Q2W dosing. The OL-RD cohorts will aim to evaluate a Q4W dosing regimen. Subjects will receive premedication prior to the treatment infusion to prevent hypersensitivity reactions, in line with previously established programs evaluating RNA therapeutics.

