7.2. Duration

7.2.1. Duration of Subject Participation

SAD Cohorts

Screening is approximately 2 weeks. After screening and dosing, subjects will be monitored for 90 days after dosing.

OL-RD Cohorts

Subjects who have completed participation in a SAD cohort, consisting of screening and a 90-day Follow-up Period, may enter an OL-RD cohort. These subjects are rescreened for participation in the OL-RD cohorts, which is expected to occur over the course of approximately 3 weeks prior to redosing; eligibility for additional dosing in the OL-RD cohorts can be combined with assessments at the SAD Day 90 Visit. After rescreening, subjects will receive a total of 4 additional doses of UX053, with doses administered Q4W, and will be monitored for 36 weeks (Week 48 Visit) after their last dose of UX053.

DB-RD Cohorts

Screening is approximately 8 to 12 weeks. Due to the staggered nature of the cohorts, subjects may remain in nutrition stabilization during screening for \geq 6 weeks. After screening, subjects will receive a total of 5 doses of UX053, with doses administered Q2W, and will be monitored for 40 weeks (Week 48 Visit) after the last dose of study drug.

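### Protocol Table 6 shows Week 10 as a dosing visit (footnote d and a sixth dosing mark) against five planned doses ending at Week 8; Table 5 footnote d words Week 16 the same way against four doses ending at Week 12

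*Protocol*

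**What the plan says.** **DB-RD cohorts.** Protocol Section 7.1 states: "DB-RD subjects will receive study drug Q2W; a total of 5 doses of study drug are planned". Section 7.2.1 repeats the count of five and adds that subjects are "monitored for 40 weeks (Week 48 Visit) after the last dose of study drug". In Table 8 the last infusion with a PK profile is Week 8. Footnote f to Table 6 ties the PK samples to the Week 0 and Week 8 infusions and restricts the 28-day sample, at Week 12, to the Week 8 infusion.

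Table 6 itself reads differently in two places. Its dosing row appears in the machine-read text as "Drug Administration X X X X X X". Its footnote d puts pre-dose assessments on the day of dosing or "on the day before dosing for visits that include a CFC (ie, W10".

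**OL-RD cohorts.** Section 7.1 says that "subjects in the OL-RD cohorts will receive 4 additional OL doses of UX053 Q4W", and Section 7.2.1 gives 36 weeks from the last dose to the Week 48 Visit. The Table 5 dosing row has four marks, at Weeks 0, 4, 8 and 12. Footnote d to Table 5 nevertheless uses the phrase "on the day before dosing for visits that include a CFC (ie, W16".

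**SAP.** The vital-sign table in Section 10.3 lists repeat-dose infusions at Weeks 0, 2, 4, 6 and 8 only. The SAP refers to the protocol of 3 January 2022, which precedes the current amendment. Section 8 says the study terminated after four subjects each had enrolled in Cohorts 1S and 2S, and that only those cohorts are analysed.

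**The concern.** The schedule of events tells a site what happens at each visit. A site that read the Table 6 row and footnote d literally could prepare an infusion at Week 10 that the design text does not contain. That would be an unplanned exposure in a first-in-human study. Section 7.1.4 also bases its dose rationale on "The NOAEL in repeat-dose studies with 5 total doses of UX053 administered Q2W", so a sixth dose would be one more than those studies gave.

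The data would change as well. Week 10 carries the optional controlled fasting challenge (CFC) and the Day 14 PK sample after the Week 8 infusion. Table 8 tells sites to draw the Week 2 sample before dosing, because DB-RD subjects are dosed that day. It gives no such instruction for the sample at Week 10. A Week 10 infusion would also contaminate the Week 12 sample, which is meant to be the 28-day point after the last profiled infusion.

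**Working it through.** **1. Dose counts and follow-up.** Inputs are the dose numbers and intervals in Sections 7.1 and 7.2.1, the marks in the two dosing rows, and the final visit at Week 48. The formulas are: last dose week = (doses − 1) × interval, and follow-up = 48 − last dose week.

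| Reading | Doses | Last dose | Weeks to Week 48 | Stated in 7.2.1 |
|---|---|---|---|---|
| DB-RD, design text | 5 | (5 − 1) × 2 = Week 8 | 48 − 8 = 40 | 40 |
| DB-RD, Table 6 row as read | 6 | (6 − 1) × 2 = Week 10 | 48 − 10 = 38 | 40 |
| OL-RD, design text and Table 5 row | 4 | (4 − 1) × 4 = Week 12 | 48 − 12 = 36 | 36 |
| OL-RD, if Week 16 were dosed | 5 | (5 − 1) × 4 = Week 16 | 48 − 16 = 32 | 36 |

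The stated 40 and 36 weeks reproduce only with last doses at Week 8 and Week 12.

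**2. What a Week 10 dose would change in DB-RD.**
- Doses: 6/5 = 1.2, or 20% more doses per subject.
- Week 12 PK sample: (12 − 8) × 7 = 28 days after a Week 8 infusion, but (12 − 10) × 7 = 14 days after a Week 10 infusion.
- Duration of exposure under SAP Section 5.2 (last dose − first dose + 14 days): 8 × 7 + 14 = 70 days with five doses; 10 × 7 + 14 = 84 days with six.

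**3. Table 6 read against itself.**
- *Pointing to dosing at Week 10:* the sixth mark in the Drug Administration row, and the wording of footnote d.
- *Pointing to a last dose at Week 8:* vital signs carry the infusion superscript e five times, at Weeks 0 to 8, with a plain mark at Week 10. Physical exam, weight and PT/INR carry the pre-dose superscript d five times, also with a plain mark at Week 10. The complement/IL-6 and fibrinogen/d-dimer rows carry superscript g (pre-dose and end of infusion) five times. Anti-drug antibodies and capillary ketones carry d five times. Footnote f treats Week 8 as the infusion that precedes the Week 12 sample.
- *Not informative:* hematology, chemistry and urinalysis carry superscript d at Week 10. In Table 5 the same rows carry d at Week 14, which is a home visit without drug administration, so the superscript does not reliably identify a dosing visit.

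**4. The CFC clause.** Section 10.5.1 places the CFC at the Stabilization Visit and at Week 10 (DB-RD) or Week 16 (OL-RD). With last doses at Week 8 and Week 12, no CFC visit is a dosing visit, so the clause in footnote d would describe nothing in either table.

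**The case against.** The strongest reply is that this is loose footnote wording plus one doubtful table mark. Several rows of Table 6 are displaced in the machine-read text: CFC, liver MRI and the PROMIS questionnaires fall under Week 12, and anti-drug antibodies start one column late. A shift of columns would not turn five marks into six, but a spurious mark in a strictly alternating row cannot be excluded without the source page. Footnote d is also weak support for a sixth dose, because the same clause appears in Table 5, where the row and the design text agree on four. And a site that tried to dose at Week 10 would find no infusion vital signs and no end-of-infusion complement sampling scheduled for that visit.

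Most of this stands, and it limits the point. It does not remove it: footnote d is running prose in both tables, does not depend on column positions, and cannot be squared with Sections 7.1 and 7.2.1.

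Three stronger readings are tempting, and the documents do not support them:
- *A reader might infer that both repeat-dose schedules show a different number of doses from the design text.* For OL-RD they do not: the Table 5 row, the text and the 36-week follow-up all agree on four.
- *A reader might take the superscript-d laboratory marks at Week 10 as independent confirmation of a sixth dose.* The Table 5 marks at Week 14 show that they are not.
- *A reader might conclude that the trial plans more doses than its repeat-dose toxicology studies gave.* Section 7.1 plans five, so this would follow only if the sixth mark were acted on.

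**Conclusion.** The inconsistency is real and should be corrected. For DB-RD, footnote d and, as read, the dosing row of Table 6 put an infusion at Week 10. Sections 7.1 and 7.2.1, footnote f, Table 8 and most infusion-linked rows of Table 6 end dosing at Week 8. The difference is one dose (6 against 5), two weeks of follow-up (38 against 40) and the spacing of the Week 12 PK sample (14 against 28 days). For OL-RD the conflict is one footnote clause.

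The Table 6 row count assumes that the machine-read row matches the printed page; the footnote conflict does not need that assumption. The exposure and follow-up figures apply only if a site dosed at Week 10. No position is taken here on which dose count is right.

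The practical effect is limited. SAP Section 8 confines the analysis to Cohorts 1S and 2S, so no planned repeat-dose result is affected. The point matters mainly for the accuracy of the protocol and for any later repeat-dose protocol drawn from it.

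**What to change.** 1. Check the Table 6 Drug Administration row against the source page and establish whether it has five or six marks.
2. Reconcile that row, and the footnote d wording in Tables 5 and 6, with Sections 7.1 and 7.2.1, so that one dose count and one set of dosing visits appears throughout for each cohort type.
3. Tidy the superscript-d marks in the laboratory rows (Week 10 in Table 6, Week 14 in Table 5) in the same edit.

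The cost is one table row, two footnotes and a few superscripts. If the count in Sections 7.1 and 7.2.1 is retained, no visit, sample or analysis has to change. If no further amendment is issued, the correction should be made before the schedule is reused elsewhere.

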4. LIST OF ABBREVIATIONS AND DEFINITION OF TERMS

Abbreviation	Definition or Explanation
ADA	anti-drug antibody
AE	adverse event
AGL	amylo- α -1,6-glucosidase 4-alpha-glucanotransferase
AH50	alternative complement activity
ALP	alkaline phosphatase
ALT	alanine aminotransferase
ApoE	apolipoprotein E
AST	aspartate aminotransferase
ASTCT	American Society for Transplantation and Cellular Therapy
AUC	area under the concentration-time curve
AUC _{inf}	AUC from time 0 to infinity
AUC _{last}	AUC from time 0 to the last measurable concentration
AUC _{tau}	AUC from time 0 to end of dosing period
BNP	B-type natriuretic peptide
BL	Baseline
BUN	blood urea nitrogen
CBC/diff	complete blood count with differential
CFC	controlled fasting challenge
CGM	continuous glucose monitor
CH50	classical pathway complement activity
CK	creatinine kinase
CK-M/B	CK – muscle/brain
CL	Clearance
C _{max}	maximum observed concentration
COVID-19	coronavirus disease 2019
CRF	case report form
CRP	C-reactive protein
CRS	Cytokine Release Syndrome
CTCAE	Common Terminology Criteria for Adverse Events
CYP2B6	cytochrome P450 2B6
DB	double blind
DMC	Data Monitoring Committee
CCI	

Abbreviation	Definition or Explanation
DPIA	Data Privacy Impact Assessment
CCI	[REDACTED]
ECG	Electrocardiogram
EDC	electronic data capture
EF	ejection fraction
EOS	end of study
ET	early termination
EU	European Union
EudraCT	European Union Drug Regulating Authorities Clinical Trials
FDA	Food and Drug Administration
FFP	fresh frozen plasma
FIH	first-in-human
FSH	follicle stimulating hormone
GCP	Good Clinical Practice
GDE	glycogen debranching enzyme
GDPR	General Data Protection Regulation
GFR	glomerular filtration rate
GGT	gamma-glutamyl transferase
Glc ₄	glucose tetrasaccharide
glycoNOE	glycogen nuclear overhauser enhancement
GNEM-FAS	GNE Myopathy Functional Activities Scale
GMP	Good Manufacturing Practices
GSD	glycogen storage disease
HDL	high density lipoprotein
HED	human equivalent dose
HEENT	head, eyes, ears, nose, and throat
HHD	handheld dynamometry
HHG	Handheld glucometer
IB	Investigator's Brochure
ICF	informed consent form
ICH	International Council for Harmonisation of Technical Requirements for Pharmaceuticals for Human Use
IEC	Independent Ethics Committee
IL-6	Interleukin-6
IND	Investigational New Drug (application)

Abbreviation	Definition or Explanation
INR	international normalized ratio
IP	investigational product
IRB	Institutional Review Board
IRR	infusion-related reaction
IRT	interactive response technology
ISV	Initial Screening Visit
IV	intravenous
CCI	[REDACTED]
LDH	lactate dehydrogenase
LDL	low density lipoprotein
LDL-R	low density lipoprotein-receptor
LNP	lipid nanoparticle
LVH	left ventricular hypertrophy
MCH	mean corpuscular hemoglobin
MCHC	MCH concentration
MCV	mean corpuscular volume
MedDRA	Medical Dictionary for Regulatory Activities
MELD	Model for End Stage Liver Disease
MRI	magnetic resonance imaging
MRS	magnetic resonance spectroscopy
MTD	maximum tolerated dose
NIAID FAAN	National Institute of Allergy and Infectious Diseases/Food Allergy and Anaphylaxis Network
NOAEL	no-observed adverse effect level
NOV	Nutrition Optimization Visit
NYHA	New York Heart Association
OL	open label
PBMC	peripheral blood mononuclear cell
PD	pharmacodynamic(s)
CCI	[REDACTED]
PK	pharmacokinetic(s)
PP	Per Protocol
PROMIS	Patient-reported Outcomes Measurement Information System
PT	prothrombin time
Q2W	every 2 weeks

Abbreviation	Definition or Explanation
Q4W	every 4 weeks
R _{AUC}	accumulation ratio (calculated as AUC after repeat dose / AUC after a single dose)
RBC	red blood cells
RD	repeat dose
RT-PCR	real time – polymerase chain reaction
SAD	single ascending dose
SAE	serious adverse event
SAP	statistical analysis plan
sC5b-9	soluble Complement 5b-9
SF-36v2	Short Form Health Survey 36 version 2
SOC	System Organ Class
STV	Stabilization Visit
SUSAR	suspected unexpected serious adverse reaction
T _{1/2}	half life
TEAE	treatment-emergent adverse event
T _{last}	time of last measurable concentration
T _{max}	time of maximum observed concentration
ULN	upper limit of normal
US	United States
V _{ss}	volume of distribution at a steady state
WBC	white blood cell
WHO	World Health Organization

Definition of Terms

Investigational Product (IP) is defined as, “A pharmaceutical form of an active ingredient or placebo being tested or used as a reference in a clinical study, including a product with a marketing authorization when used or assembled (formulated or packaged) in a way different from the approved form, or when used for an unapproved indication, or when used to gain further information about an approved use” (from International Conference on Harmonisation of Technical Requirements for Registration of Pharmaceuticals for Human Use [ICH] Harmonised Tripartite Guideline E6: Guideline for Good Clinical Practice).

The term “study drug” may also be used in place of “investigational product” in the protocol.

